4.5 Follow up visits

Participants will be reviewed as per schedule above (2.3) and repeat samples of SWMF and blood taken. The oral health questionnaire and the whole mouth examination will not be repeated, unless there are major changes in the clinical condition. Participants will be given a window of +_ 5 days for scheduling appointments.

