Notably, recent studies support the hypothesis that the oral microbiota is of relevance in both acute and chronic lung disease, with poor oral health associated with an increased risk of respiratory disease (Mammen et al 1999). A question is, therefore, whether inflammation in the oral cavity may predispose to SARS-CoV2 infection (Sampson et al 2020). We know that improving oral health results in a reduction in respiratory infections in ICU and nursing home patients (Azarpazhooh et al 2006). Of particular relevance to the current COVID-19 pandemic, risk factors including coughing, hyperventilation and mechanical ventilation have been shown to provide a pathway for members of the oral microbiota to penetrate the lower respiratory tract and cause disease (Bao et al 2020). Co-infections have been significant causes of mortality in many previous viral pneumonia pandemics, including the recent 2009 swine flu outbreak (MacIntyre, et al 2018), and these phenomena appear to be repeating for the current COVID-19 pandemic. Early metatranscriptome analyses indicate the presence of elevated levels of oral commensal bacteria in the bronchoalveolar lavage of COVID-19 patients (Shen et al 2020).

There is increasing evidence of disparities in susceptibility to SARS-CoV-2 infection and subsequent morbidity and mortality amongst groups of different ethnic origin. In the UK, South Asian populations have been identified as a particularly susceptible group, with a high percentage mortality in contrast to similar populations in India, even after taking into account the effect of socio-economic level and of co-morbidities. The extent to which social, environmental and biological factors differ in the two populations and contribute to differences in outcomes from COVID-19 is not known.

Our research will compare the oral microbiome, salivary innate and specific mucosal antibody responses and oral disease among SARS-CoV2-positive patients and controls in the UK and determine their diagnostic and prognostic utility. We will compare mucosal and systemic immunity in order to reveal biomarkers for risk of disease progression so as to enable early initiation of treatment.

The study is part of a UK-India partnership and at the end of the research, data from the UK will be compared with that derived from a similar study with our collaborators in India.

References

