2.1. Trial Objectives

- Primary Objective

The key aim of this research in South Asian populations and White British populations, is to find out whether differences in COVID-19 morbidity and mortality in similar populations in the UK might be related to mucosal immunity expressed in the mouth and to the oral microbiome (the total bacteria, fungi and viruses living in the mouth). This will be achieved by determining

whether in the mouth there are differences between the participant groups of mucosal natural immunity (innate immunity), immune responses to SARS-COV2 antigens (adaptive immunity), or the oral microbiome

- Secondary Objectives

1. To determine whether differences in mucosal immunity or differences in the oral microbiome correlate with susceptibility to COVID-19 infection, or to progression and recovery from the disease.

2. To determine whether the presence of pre-existing oral disease is related to susceptibility to SARS-CoV2 infection, to severity of COVID-19 disease or relates to the nature of mucosal immunity and to the composition and activity of the oral microbiome

- Primary End Point

- Collection, processing and analysis of samples. Statistically significant quantitative differences in measured mucosal innate immune factors, mucosal adaptive immune factors and/or in the oral microbiome in relation to 1) a comparison between South Asian and White British populations in the UK 2) the degree of severity of COVID in South Asian and White British participants in the UK

- Secondary End point

- Generation of raw data.
- *a comparison between South Asian populations in the UK and in Chennai, India.

**Note: This is the UK part of an international research collaboration between the UK (funded by the MRC) and India (funded by the DBT) with research being carried out separately but in parallel in the two Countries and generating results which will be directly compared.*

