2.2 Trial Design & Flowchart

Proposed Methodology: In this combined cross sectional and prospective longitudinal study, non-COVID infected subjects and SARS-CoV2-positive patients of South Asian origin or White British origin diagnosed to have, or who have had, asymptomatic, mild, moderate or severe disease as per WHO or the equivalent NIH criteria will be recruited. Peripheral blood (approx 17 ml divided into 5ml clotted, 2ml EDTA, 2ml fluoride, 8ml heparinised) and stimulated whole mouth fluid (SWMF) samples (approx 4ml) will be collected from all patients and from subgroups at three further time points at approximately 2, 4 and 12 weeks. (SWMF is a combination of saliva, gingival crevicular fluid, desquamated epithelial cells, some nasopharyngeal secretions, some serum transudate). In addition to medical data available for each patient, short questionnaires on oral health and diet, a clinical examination for oral health using “PSR akaBPE” – periodontal screening and recording/basic periodontal examination of periodontal health will be undertaken. The maximum periodontal pocket depth in mm on all standing teeth using a graduated periodontal probe and the presence of bleeding on probing will be recorded for each tooth. Missing teeth will be noted.

Further information on ethnicity of South Asians will be sought, eg from Pakistan, Bangladesh, North India, South India or Sri Lankan [Sinhalese, Tamil or Muslim].

Sequence of consent, examination and samples:

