
Group 2. SA2, BW2. Asymptomatic/mild n=100 each
	
Asymptomatic/mild SARS-CoV2 positive group Volunteers or subjects attending SARS-CoV2 testing centres who are found to be antigen positive or In-patients who have positive Covid tests and designated as asymptomatic/mild but admitted for non-covid reasons or those attending A&E with COVID but designated as mild/asymptomatic will be furnished with the participant information leaflet and invited to take part in the study After obtaining informed consent, oral examination, oral health & medical history questionnaires and blood and stimulated whole mouth fluid (SWMF) (see below) will be taken at the department of Oral Medicine at Guys Hospital or on the wards or in A&E at GSTT and KCH. Groups of 100 South Asian and White British participants will be recruited.

Groups 3 SA3, BW3 n=100 each
	
Moderate/Severe Symptomatic patients Patients either seen at GSTT or admitted as in-patients to GSTT or KCH and found to be SARS-CoV2 positive by RT-PCR in nasopharyngeal samples and designated as moderate/severe on the NIH/NIMR COVID severity scale will be furnished with the participant information leaflet and invited to take part in the study and will be enrolled in the study after obtaining written informed consent. After obtaining informed consent, oral examination, oral health & medical history questionnaires and blood and stimulated whole mouth fluid (SWMF) (see below) will be taken at the department of Oral Medicine at Guys Hospital or on the wards or in A&E. Groups of 100 South Asian and White British participants will be recruited.

Groups 4. SA4, BW4 n=100 each
	
'Recovered' patients These will be patients who have had COVID. They may be invited directly to participate by advertising at sites specified above or be attending either the post-COVID or ICU follow-up outpatient clinics. Patients may cover the COVID severity range and include those with a severe/moderate COVID history. Those attending the post-COVID clinic may include those referred in by primary care including those with long-COVID. Covid positive patients discharged from GSTT and fulfilling the inclusion criteria will be sent letters of invitation to participate. This data is available to the COVID clinical research team and participants will be identified with the Clinical Research Dentist.

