Relevant Medical history including current medication

Relevant Dental History

Mouth Examination (this will include any previous dental habits)

"PSR/BPE" – periodontal screening and recording/basic periodontal examination.

Adverse Events,

The CRF will also have a withdrawal from study form which will record participants reason for withdrawal when/if known.

Patient Metadata and tissue collection form

Sample ID

Date of collection

Time of collection

Initials of clinician undertaking

Patient Metadata

Age of patient

Sex M/F

Oral Hygiene Habits

Does Patient use toothpaste yes/ no

Patient regularly sees dentist yes/no

History of previous periodontitis yes /no
 If yes to give further details
 If patient is a smoker (standard cigarettes) yes/ no
 Patient smokes e-cigarettes yes/ no

Sample collection

SWMF: stimulated whole mouth fluid sample yes/no
 Volume of SWMF collected (to be detailed at laboratory)
 Blood samples yes/no

The CRF will be updated at all 3 study visits.

The CRF will be completed by the primary investigator at all study visits as well as any named staff working on the trial. All participants will be added to an enrolment log.

Record Retention and Archiving

Source documents containing or relating to clinical data will be kept for five (5) years after termination of the study. The Principal Investigator will maintain study documentation for all participants entered into the study in a secured, locked and alarmed room, ensuring the confidentiality of the information collected. Securing records includes placing written forms in locked file cabinets and/or sealed and labelled storage boxes in a locked room and alarmed room. Access will be denied to all persons with the exception of the Principal Investigator and his designees. Pseudo-anonymised data derived from the study will be kept for 10 years and then archived by Kings College London.

Compliance

The CI will ensure that the trial is conducted in compliance with the principles of the Declaration of Helsinki (1996), and in accordance with all applicable regulatory requirements including but not limited to the Research Governance Framework, Trust and Research Office policies and procedures and any subsequent amendments.

11. Finance and Publication Policy

The intention is for findings from the study to be published in appropriate peer-reviewed scientific journals. Summary findings will be placed on the study website <https://www.kcl.ac.uk/research/mimsa>

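### The protocol promises prognostic and progression biomarkers, but specifies COVID severity only as a label at entry and no severity grade or clinical outcome for systematic collection at follow-up

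*Protocol*

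**What the plan says.** **The aims.** The title claims diagnostic and prognostic utility. The Introduction says the study will compare microbiome, antibody responses and oral disease between patients and controls and "determine their diagnostic and prognostic utility". It adds that comparing mucosal with systemic immunity should "reveal biomarkers for risk of disease progression so as to enable early initiation of treatment". Secondary objective 1 (section 2.1) asks whether marker differences "correlate with susceptibility to COVID-19 infection, or to progression and recovery from the disease". The severity part of the primary end point, also in 2.1, concerns marker differences in relation to "the degree of severity of COVID in South Asian and White British participants in the UK".

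**When severity is assigned.** Section 2.2 states that people "diagnosed to have, or who have had, asymptomatic, mild, moderate or severe disease as per WHO or the equivalent NIH criteria will be recruited". In the subject selection table of section 3, group 3 participants are already "designated as moderate/severe on the NIH/NIMR COVID severity scale" before they receive the information leaflet. Group 2 is likewise recruited as asymptomatic/mild. Inpatients may enter up to 21 days after symptom onset (section 3.1).

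**What follow-up collects.** Section 4.5: "Participants will be reviewed as per schedule above (2.3) and repeat samples of SWMF and blood taken". The oral questionnaire and mouth examination are repeated only on major clinical change. The Case Report Form part of section 10 lists basic clinical parameters and safety, demographics, medical history and medication, dental items, adverse events and sample data, and adds: "The CRF will be updated at all 3 study visits". No listed item is a COVID severity grade, admission, escalation, recovery or death.

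**The concern.** A statement about prognosis or risk of progression needs a marker measured first and a clinical state observed later. The protocol specifies the first and not the second.

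Its own disease model (figure legend, section 1) makes the order important. A virological phase of about 5 to 7 days comes first, and a prolonged immune response then drives severe disease. Someone sampled while mild may worsen afterwards. Group 3 is first sampled once moderate or severe. A marker that differs between groups 2 and 3 could be a cause of severe disease, a consequence of it, or an early warning, and the entry label cannot separate these.

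At stake is the use the Introduction has in mind. A marker could be put forward to guide early treatment on the strength of a contrast between states already reached, with no planned analysis of anyone's later course.

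**Working it through.** **1. Set each claim against the data it needs.**

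| Claim | Needs | Specified? |
|---|---|---|
| Marker differences by degree of severity (2.1, primary end point) | Grade at sampling | Yes, as the entry group |
| Correlation with progression (2.1, secondary objective 1) | Change in grade after the baseline sample | No |
| Correlation with recovery (same) | Later fall in grade, or a recovery outcome | No |
| Risk of disease progression, prognostic utility (section 1) | Baseline marker and later outcome | Baseline marker only |

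Section 5.1 plans to correlate longitudinal immune responses and microbiota shifts with severity, but the only severity value specified is the entry label. That analysis describes marker kinetics within entry groups. The recovered groups enter with past severity only, so their samples cannot precede the illness whose course would be predicted.

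**2. How much could be learned if progression were recorded?** The protocol gives no progression rate and no accuracy target. Both are assumed here: 2%, 5%, 10% or 15% of group 2 progress, and a marker has a true AUC of 0.75.

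Hanley-McNeil variance with *e* progressors and *m* non-progressors:

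Var = [A(1−A) + (e−1)(Qa−A²) + (m−1)(Qb−A²)] / (e·m), where Qa = A/(2−A) and Qb = 2A²/(1+A).

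For A = 0.75: A(1−A) = 0.1875, Qa−A² = 0.6000−0.5625 = 0.0375, and Qb−A² = 0.6429−0.5625 = 0.0804.

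Worked case, 200 people and 4 events: (0.1875 + 3×0.0375 + 195×0.0804)/(4×196) = 0.0204, so SE = 0.143. The interval 0.75 ± 1.96×0.143 is 0.47 to 1.03, capped at 1.00.

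Two bases matter. Group 2 holds up to 2×100 = 200 people, all assayed for immunology at baseline. Under 2.2, only the first 50 in each group are invited for sequential samples and go to microbiome analysis, so 2×50 = 100. (Section 5.1 allows microbiome analysis on 50 to 100 per group, so 100 is the lower figure for the baseline microbiome.)

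| Assumed rate | Events of 200 | SE | 95% CI | Events of 100 | SE | 95% CI |
|---|---|---|---|---|---|---|
| 2% | 4 | 0.143 | 0.47-1.00 | 2 | 0.202 | 0.35-1.00 |
| 5% | 10 | 0.091 | 0.57-0.93 | 5 | 0.129 | 0.50-1.00 |
| 10% | 20 | 0.065 | 0.62-0.88 | 10 | 0.092 | 0.57-0.93 |
| 15% | 30 | 0.054 | 0.64-0.86 | 15 | 0.076 | 0.60-0.90 |

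With very few events the normal approximation is rough, so the first row shows only that almost nothing could be concluded. Group 3 participants not yet at the top grade would add events; the protocol gives no basis for counting them.

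**The case against.** **Some outcomes will surface.** Section 6.2 requires SAEs to be recorded even when apparently unrelated to the study. The CRF has a basic clinical parameters heading and is updated at visits, section 4.4 puts ward and follow-up visits into the hospital record, and 2.2 refers to medical data available for each patient. This stands: a reader might infer that no outcome at all is captured, and the text does not support that. But none of these sources names a COVID severity or outcome field, and none is linked to an analysis.

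**The CRF list is not exhaustive.** It also omits baseline severity, symptom onset and PCR date, on which grouping and eligibility depend. Absence from the list therefore does not prove non-collection. The point rests on the list together with section 4.5 and the end points, none of which specifies a later severity or outcome.

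**The primary end point is unharmed.** A reader might infer that people who worsen later dilute the severity contrast. They do not. Someone mild when sampled is correctly mild in a cross-sectional comparison, and 2.1 does not ask for worst later grade.

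**Group 2 is not the only source of progression.** Group 3 includes moderate cases and, by section 3, people only planned for admission; they can worsen or recover.

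**The analysis plan could handle this.** It could settle how a change of grade is treated, on which the protocol is silent; the protocol does not say that a worsening participant is analysed as mild. It cannot supply an outcome that was not systematically collected.

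**Conclusion.** The point holds for secondary objective 1, the title and the prognostic statements in the Introduction. As specified, the severity comparison supports association with severity at sampling and nothing about later course. It does not undermine the primary cross-sectional end point.

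The gap is in specified, systematic collection; some events may still be found in safety reports or hospital notes. If it were closed, estimates would be modest. Under the assumed 2% to 15% progression in group 2 and a true AUC of 0.75, even the best case has a 95% CI of 0.64-0.86 with outcomes on all 200, and 0.60-0.90 in 100. At 2% neither base is informative. The rates and the AUC are assumptions, not figures from the protocol. The sponsor should correct this before the prognostic claims are relied on.

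**What to change.** - **Section 4.5 and the CRF:** record the WHO/NIH grade at baseline and at each follow-up visit. Record admission, escalation, recovery and death to week 12 from the hospital record or by a question at the visit.
- **Definitions:** progression is a rise in grade after the baseline sample and recovery is a fall. Apply progression to group 2 and to group 3 participants not yet at the top grade. Keep grade at sampling for the cross-sectional contrast.
- **Claims:** base prognostic or risk-of-progression statements only on baseline markers v later change. Describe the group 2 v group 3 contrast as association with current severity.
- **If outcomes cannot be added:** reword the title, Introduction and secondary objective 1 to association with severity at sampling.

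**Cost:** a few CRF fields, a record check and protocol wording, with no extra visits or samples. Events may be few, more so given the ambulant recruitment and vaccination described in 2.2. Capture will be incomplete: a question at the visit cannot reach those with a single visit (up to 200 − 100 = 100 people in group 2), and the trust's record may miss admissions elsewhere. The share of participants with known week 12 status should therefore be reported beside any prognostic result.

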4.6 End of Study Definition

For subjects in cross sectional study– when collection and analysis of samples has been completed.

For subjects in the sequential study, following two or three further visits and sample collection. When target numbers of SWMF and blood samples have been processed and analysed.

5. Laboratories (if Applicable)

5.1 Central/Local Laboratories

Blood samples designated for routine blood tests and glucose will be sent to the hospital blood pathology lab for processing and analysis according to routine processes.

The remaining blood samples will be processed and prepared in the Centre for Host Microbiome laboratory on [name], Guy’s Hospital. Microbial DNA extraction will be performed in these laboratories. Extracted microbial DNA identified by study number only will be sequenced by specialised commercial companies or academic institutions in the UK or non UK.

The salivary microbiome will be analysed on 50-100 patients per group after microbial DNA extraction with standardised protocol, using shotgun metagenomic sequencing on an Illumina NovoSeq generating > 20 million reads/sample. Sequencing will be performed by a commercial provider. Analysis of the sequencing data will be performed at KCL under the supervision of CHMI academics as described in section 2.4. The salivary metabolome will be determined using NMR. The longitudinal immune response and shifts in the oral microbiota will be correlated with COVID-19 severity as well as both COVID-19 and non-COVID-19 oral disease. We will identify significant differences in oral microbiota & immune responses during transition from viral to immunological to post-COVID-19 phases, identifying specific host factors as therapeutic targets.

Salivary secretory IgA antibody assay to study mucosal responses to antigens associated with COVID-19.

SARS is a closely related virus to SARS-CoV2. Several crystal structures have been published that describe how different antigens recognize the SARS spike protein receptor binding domain. These highlighted antigenic regions in the SARS spike protein. Structures are also now available for the homologous SARS-CoV2 spike protein receptor binding domain. The amino acid sequence of the spike protein from SARS & SARS-CoV2 were compared. Major differences were identified and 10 peptides constructed. Three of these have been selected and will be assayed by ELISA along with Capsid antigens obtained commercially. The group has extensive experience with ELISA techniques, and has performed preliminary experiments to verify their use in SWMF. (This kit has been developed and validated in King's College London, and methodology shared with VHS, Chennai for sample testing.)

Blood and SWMF lymphocyte phenotyping

Blood and SWMF pellet T cell phenotyping will be performed by flow cytometry (BD FACSLyric) using monoclonal antibodies (BD Biosciences) to T cell markers. Pan T cells – CD3; Helper T cells – CD4; CD4 T cell activation marker – CD25; Cytotoxic T cells – CD8; CD8 T cell activation marker – CD38; NK cells – CD56 and HLA-DR; Th17 and Th22 cells – CCR4, CCR10; Tfh cells - ICOS; Tregs – Foxp3; T cell exhaustion marker – PD-1; effector and memory T cells – CD45RA and CD45RO/CCR7; mucosal homing marker – CD69; airway homing marker – integrin β 1 and β 7. T cell phenotypes will be reported as percentages of the total T cells. Cells will be stained with the defined cocktail of antibodies for 15 minutes at room temperature in the dark; fixed and permeabilised; and then stained with intracellular antibodies (as appropriate) for 15 minutes; washed and analysed by flow cytometry.

For SWMF analysis, the samples will be gently centrifuged and a portion of the pellet resuspended in buffered saline, and incubated with the fluoresceinated antibodies before passing through an analyser.

Cytokine profiles will be analysed and quantified using the CBA kits (BD Biosciences) as per the manufacturer's instructions. Cytokines include IL-2, IL-4, IL-6, TNF- α , IL-1 β , IFN- γ , IL-17, IL-22, IL-23, IL-8, IL-12p70, TGF- β , IP-10, MIG, MCP-1, CCL-20. CBAs will be analysed by flow cytometry (BD FACSLyric). Total IgG will be detected in the serum/plasma and SWMF supernatant samples by ELISA as per the manufacturer's instructions.

All of the techniques have been established, used and validated in the CHMI laboratories.

